5.3. Detail of the study assessments

5.3.1. Physical Examination and Vital Signs

A routine physical examination (including body weight) will be done at each study visit. Physical examinations will cover eyes, ears, nose, throat, lungs/thorax, heart/cardiovascular system, abdomen, skin and mucosae, nervous system, lymph nodes, musculo-skeletal system, and, if applicable, others. Any new clinically relevant finding compared to baseline must be documented as adverse event.

Measurements of vital signs will be done at each visit (Blood pressure, Heart Rate, Body temperature). The subject should rest supine for at least 10 minutes prior to measurements. The measurements can be performed either in sitting or supine position of the subject. The right or left arm may be used. However, the position and the arm used for measurement should be kept constant throughout the trial for an individual subject.

The investigator should ensure that each parameter outside the normal range is assessed for clinical significance. For any deviation assessed clinically significant, the investigator has to document the change as an AE in the CRF.

In addition, it is at the discretion of the investigator to document any change or trend over time in vital signs as an AE if he considers the change to be clinically significant, even if the absolute value is within the alert limit or reference range.

5.3.2. Pregnancy

For all female subjects of childbearing potential, a blood pregnancy test (beta human chorionic gonadotropin [HCG]) will be performed at Day -14, Day 0, Day 28, Day 56. In case of positive pregnancy testing, detailed procedures can be found in section 8.3.2.

5.3.3, ECG

Electrocardiograms have to be done at Day -14, Day 0, Day 28, Day 56 and EoS visit. At least a 12-lead ECG with recordings of at least 6 action potentials in lead II (paper speed 25mm/s, amplitude 10mm/mV) has to be done in a resting position. Prior to the recording the subject should be at rest for at least five minutes. Resting ECG should be performed before any examinations.

The ECG printout will be reviewed by the investigator and a signed and dated copy of the ECG will be attached to the medical file. The original ECG printouts are considered as source data and should be stored at site. In case thermal paper is used, a copy of the original ECG must be kept as well. All abnormal findings must be documented in the CRF. Any clinically relevant findings compared to ECG done at Day 0 must be documented as adverse events.

5.3.4. SF-36 questionnaire (SF-36)

The SF-36 questionnaire is a self-administered questionnaire containing 36 items which takes about five minutes to complete. It measures health on eight multi-item dimensions, covering functional status, well-being, and overall evaluation of health. SF-36 will be filled in by the subjects at Day 0, Day 28 and Day 56 prior to any study procedures.

5.3.5. Partial/Total Mayo Score

The Mayo score is the most commonly used index in clinical trials and consists of 4 items: stool frequency, rectal bleeding, flexible sigmoidoscopic examination, and a physician global assessment (Appendix#3).

A non-invasive 9-point Mayo or partial Mayo incorporates stool frequency, rectal bleeding, and the physician's global assessment. The partial Mayo has been found to correlate closely with the full Mayo score and to independently have strong discriminative and construct validity and responsiveness to change in disease activity.

Either the Partial or the Total Mayo score will be completed at each subject visit by the Investigator.

5.3.6. Sigmoidoscopy with rectal/sigmoidal biopsies

Sigmoidoscopies procedures will be standardized for optimized video acquisition at clinical sites. Sigmoidoscopies should be performed according to the Central Imaging Management System Charter.

Central Imaging Management System will be provided including a central image database. Once uploaded, video data will be analyzed for quality and resolution prior to independent review by an expert central reader.

Study videos will be scored separately using the Mayo Clinic Score for all time points by a single central reader who is blinded to the treatment and visit sequence of the recordings. The central reader's score at Screening and Week 8 will be entered into the eCRF. Screening videos will be evaluated for eligibility and scores communicated to sites within four (4) business days. All procedure videos collected for outcome evaluation will be scored and results communicated within five (5) business days.

Two rectal biopsies (plus optionally two sigmoidal biopsies, if the inflammation of the sigmoid is observed) will be performed at screening and at Week 8. The two biopsies will be sent to the central laboratory for Geboes score determination (please refer to the lab manual) and for miRNA-124 determination (RNA later).

5.3.7. Hematology and biochemistry

For hematology and biochemistry central laboratory will be used (i.e. Eurofins). All lab dosages will be done centrally except the ESR that need to be done locally. Devices will be anyway provided by Eurofins. Regarding the calprotectin sample, the site will be asked to keep samples at -80°C till the end of the study.

Each laboratory value that is outside of the normal range will be identified. The investigator will be responsible for assessing the clinical significance of laboratory abnormalities. If the investigator is uncertain about the clinical significance of a laboratory abnormality, he/she will consult with the Sponsor medical monitor. The investigator should follow any clinically significant laboratory abnormalities until resolution.

Table 1 displays the clinical laboratory parameters that must be measured.

Table 1: Laboratory Tests

HEMATOLOGY	BIOCHEMISTRY	Stools
Hemoglobin	Sodium	Faecal calprotectin
Hematocrit	Potassium	
WBC	Chloride	
Neutrophils	Calcium	
Lymphocytes	Phosphate	
Monocytes	Glucose	
Eosinophils	BUN or urea	*****
Basophils	Creatinine	
Platelet count	AST	
ESR	ALT	
	GLDH	
	Lipase	
	Alkaline phosphatase	
	gGT	
	Total bilirubin	
	Total protein	
	Albumin	
	LOH	
	CRP	

At each biochemistry time point, a tube containing the remaining serum (at least 1 mL) should be kept and stored at -20°C for potential further liver function parameters such as soluble caspase-cleaved keratin 18 (M30 Elisa) and/or miRNA22 as a marker of early hepatotoxicity.

5.3.8. miRNA modulation

ABX464 up-regulates miRNA in PBMCs, making of this micro-RNA a potentially useful biomarker for ABX464 treatment monitoring. Determination of miRNA level in whole blood and in tissue will be performed in order to assess treatment effect by comparing before and after treatment. Assays for miRNA determination and tropism test will be conducted by ACOBIOM.

Blood will be collected in PAXgene® tubes according to lab manual instructions. The rectal/sigmoidal biopsies will be stored in RNA later according to lab manual instructions.

5.3.9. Microbiome assays

The microbiome composition might affect the reservoir size and is key to mucosal immunity. Microbiome specimen will be collected using a rectal swab before each flexible sigmoidoscopy procedure. The microbiota will be characterized by ACOBIOM at screening and at Day 56 using 16S rDNA Illumina (R) deep sequencing and analyzed using similar methods.

5.3.10. Pharmacokinetics

The main objective of the PK analysis is to evaluate potential PK specificities of ABX464 in subjects suffering from active UC.

ABX464 was shown to have a very short $t_{1/2}$ (1 to 2 h), so steady-state is virtually reached at the second administration, while NGlcABX464 has a $t_{1/2}$ of 90 to 110 h, meaning that steady-state is reached after 19 to 22 days of administration.

PK analysis will be performed in the first 9 subjects enrolled in this study at Week 0 and Week 4. A first blood sample (reference) will be collected on the first day of treatment before any drug administration then blood samples will be collected for PK purpose at, 0.5, 1, 1.5, 2, 2.5, 3, 4, 8 and 12 post-dose samples

A total of 10 blood samples per subject will be collected for PK purpose and sent to ATLANBIO for Bioanalyses.

Study code: ABX464-101

Blood samples for determination of ABX464, NGlcABX464, Hydroxyl ABX464 glucuronide and/ will be collected from all subjects using direct venipuncture or an indwelling catheter.

Then, the following PK parameters will be derived for ABX464 and NGlcABX464 for each subject:

- C_{max}, t_{max}: the maximum plasma concentration (C_{max}) and the time taken to reach C_{max} (t_{max}) will be obtained directly from the concentration-time data.
- AUC_{0-τ}: the area under the concentration-time curve from time zero to the time of dosing interval τ (12 h post-dose for ABX464 and NGIcABX464). If no concentration can be measured at this time point, AUC_{0-last} (from time zero to the last quantifiable concentration) will be calculated. Both parameters will be presented independently. For both parameters, a linear trapezoidal method will be used.

Moreover, evaluation of steady-state will be made by visual inspection of the pre-dose concentration measurement collected over the study duration.

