3. INVESTIGATIONAL PLAN

3.1. Study design

3.1.1. Design and methodology

This Phase IIa study is an 8-week, double-blind, placebo-controlled, randomized study aimed at evaluating the safety and the efficacy of ABX464 given once a day (o.d) at 50 mg in subjects with moderate to severe Active Ulcerative Colitis who have failed or are intolerant to immunomodulators, Anti-TNF α , vedolizumab and/or corticosteroids followed by a one-month follow-up period.

Eligible subjects will be randomized according to a 2/1 ratio in two different groups of treatments according to the following study design.

Upon screening visit (D-14), eligible subjects will be checked for eligibility.

Subject eligibility will be confirmed by the medical staff based of the endoscopy central reading and on the laboratory results performed at screening visit. If eligibility is confirmed, then the subject will be randomized using the eCRF.

At Day 0, study drug (ABX464 or its matching placebo) will be added on top of this background therapy for the next 56 days. ABX464 or its matching placebo will be given once a day at 50 mg.

For subjects receiving oral corticosteroids during the study treatment period, tapering of steroids should start at week 4 at a rate of prednisone or prednisone equivalent 5 mg/week for 4 weeks to discontinuation. However, this study procedure is left to the Investigator's discretion.

The dose of 50 mg of the study drug has been selected based on the reassuring safety data accumulated on the 50 mg o.d. from previous studies and the high exposure in ABX464-NGluc (active metabolite) at this dose.

Eligible subjects will be randomized according to a 2/1 ratio in two different groups of treatments.

Randomization will be stratified according to the following factors: concomitant treatment with corticosteroids and previous TNF antagonist exposure.

Randomized subjects will be seen at the investigational site every week during the first month of treatment and then every two weeks during the second month. Flexible sigmoidoscopy with rectal and/or sigmoidal biopsies will be performed again at week 8.

The DSMB will meet after every 3 subjects are recruited in order to review on a regular basis the safety profile of this dose level and to recommend, if appropriate, the continuation of the study.

The sample size in this Proof of Concept study is 20 subjects receiving ABX464 and 10 subjects receiving Placebo (i.e. a total of 30 subjects).

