6.3. Administration and Dosing

6.3.1. Administration of the investigational product

Subjects will be dosed with a daily dose of 50 mg that is 1 capsule every day.

Subjects will be orally dosed in fed condition (regular breakfast) with 240 mL of water.

A subject diary, in which the subject should report the number of capsules taken and the intake time, will be given to the subject at screening. Moreover, this diary will enable the subject to report also potential discomfort or side effects s/he could experience.

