9.2.1. Pharmacokinetics

A total of 10 blood samples per subject will be collected for PK purpose.

Individual plasma concentrations of ABX464, NGlcABX464, Hydroxyl ABX464 glucuronide, will be presented by treatment and time points. Descriptive statistics for the plasma concentrations will be presented as number of available data (N), mean, standard deviation (SD) and will be calculated if at least 2/3 of the plasma values per time-point are above LOQ (i.e. $N \ge 10$ if 15 subjects are available for a given group). For descriptive statistics calculations, BLQ concentrations below the limit of quantification will be set to zero (0) if they are reported before the first quantifiable sample or considered as missing data if they are reported after the first quantifiable data

Then, the following PK parameters will be derived for ABX464 and NGIcABX464 for each subject:

 C_{max} , t_{max} : the maximum plasma concentration (C_{max}) and the time taken to reach C_{max} (t_{max}) will be obtained directly from the concentration-time data.

AUC $_{0-\tau}$: the area under the concentration-time curve from time zero to the time of dosing interval τ (12 h postdose for ABX464 and NGlcABX464). If no concentration can be measured at this time point, AUCO-last (from time zero to the last quantifiable concentration) will be calculated. Both parameters will be presented independently. For both parameters, a linear trapezoidal method will be used.

Individual derived PK parameters will be presented by treatment and day of PK assessment when appropriate. Descriptive statistics of the PK parameters will be presented as N, mean, SD, median, minimum (Min), maximum (Max) values, and geometric mean (GM).

In the tables of individual PK parameters, all the deviations from planned analysis will be mentioned by flagging the abnormal results.

Possible exclusion of flagged PK parameters could be performed if, in the judgment of the pharmacokineticist, they are deemed not to be "pharmacokinetically relevant". Exclusion of PK parameters will be discussed in the PK results section. If data are excluded from the PK dataset, all subsequent statistical analyses will be performed twice, once using the complete available PK dataset and once using the final PK dataset as defined by the pharmacokineticist. Study conclusion will be based on the final dataset as defined by the pharmacokineticist.

For each compound, plasma concentration vs. time curves will be presented on a log-linear scale:

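### The protocol calls a 12-hour area the dosing-interval AUC under once-daily dosing, and its visual steady-state check has only one on-treatment trough to look at.

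*Protocol*

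**What the plan says.** Dosing is once daily throughout. Protocol 3.1.1 states that "ABX464 or its matching placebo will be given once a day at 50 mg", and 6.3.1 that "Subjects will be dosed with a daily dose of 50 mg that is 1 capsule every day".

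Protocol 5.3.10 nevertheless runs AUC0-τ "from time zero to the time of dosing interval τ (12 h post-dose for ABX464" and for NGlcABX464. Section 9.2.1 repeats the definition ("12 h postdose for ABX464"). The sampling schedule is pre-dose and then nine times up to 12 h; there is no 24-hour sample. AUC0-24 appears in the protocol's abbreviation list but is not among the derived parameters. SAP 4.3 leaves PK methods out, so the SAP does not settle the matter.

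On timing, 5.3.10 says "PK analysis will be performed in the first 9 subjects enrolled in this study at Week 0 and Week 4". It gives the parent a half-life of "1 to 2 h), so steady-state is virtually reached at the second administration", and the metabolite a half-life "of 90 to 110 h, meaning that steady-state is reached after 19 to 22 days of administration". Steady state is to be evaluated by "visual inspection of the pre-dose concentration measurement collected over the study duration".

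**The concern.** Two statements do not fit the rest of the plan.

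- **The label.** A dosing interval of 12 h contradicts once-daily dosing. For a compound eliminated within hours the difference is trivial. For a metabolite with a half-life of four days or so, concentrations at steady state are nearly flat across the day, so stopping at 12 h leaves out about half of the interval. Section 5.3.10 says the PK analysis looks for features specific to active UC, which invites comparison with exposure measured elsewhere. A 12-hour area called AUC0-τ, set beside a 24-hour AUC0-τ, would look like a halving of metabolite exposure in UC.
- **The steady-state check.** The wording on pre-dose samples suggests a series of troughs. PK is drawn only on Day 0 and Day 28, and the Day 0 pre-dose sample is taken before any drug. One on-treatment trough per subject remains, and a plateau cannot be seen in one point.

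**Working it through.** **Inputs from the documents.** Dosing every 24 h (3.1.1, 6.3.1); last sample 12 h post-dose, PK days 0 and 28, half-lives 1-2 h (parent) and 90-110 h (metabolite) (5.3.10 and the flow chart).

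**Assumed.** The metabolite's formation half-life is not in the documents. It was varied over 0.25, 1, 2 and 4 h, with instantaneous formation as a limiting case at steady state. The parent's absorption half-life is also not given; 0.25-0.9 h was used. Kinetics are first-order.

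**Step 1: the protocol's own figure.** Five half-lives are 5 × 90 / 24 = 18.75 days and 5 × 110 / 24 = 22.92 days. This reproduces the stated 19 to 22 days, apart from 22.9 having been cut to 22.

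**Step 2: metabolite, instantaneous formation, steady state.** With k = ln 2 / t½,

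AUC0-12 / AUC0-24 = (1 − e^(−12k)) / (1 − e^(−24k)) = 1 / (1 + 2^(−12/t½))

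- t½ = 90 h: 1 / (1 + 0.9117) = 0.523
- t½ = 110 h: 1 / (1 + 0.9272) = 0.519

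**Step 3: metabolite, gradual formation.** After n daily doses, at time t after the last one, concentration is proportional to the sum over j = 0 to n − 1 of [kf / (kf − ke)] × [e^(−ke(t+24j)) − e^(−kf(t+24j))], with ke and kf the elimination and formation rates. Integrating this for n = 1 (Day 0) and n = 29 (Day 28) gives AUC0-12 / AUC0-24:

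| Elimination t½ | Formation t½ | Day 0 | Day 28 |
|---|---|---|---|
| 90 h | 0.25 h | 0.515 | 0.522 |
| 90 h | 1 h | 0.490 | 0.518 |
| 90 h | 2 h | 0.453 | 0.513 |
| 90 h | 4 h | 0.395 | 0.506 |
| 110 h | 0.25 h | 0.511 | 0.518 |
| 110 h | 1 h | 0.486 | 0.514 |
| 110 h | 2 h | 0.450 | 0.510 |
| 110 h | 4 h | 0.392 | 0.505 |

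With Step 2 included, Day 28 spans 0.505 to 0.523. Day 0 spans 0.392 to 0.515 and depends much more on the formation rate.

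**Step 4: parent.** The Step 2 formula gives 1 / (1 + 2^(−6)) = 0.985 for 2 h and 1 / (1 + 2^(−12)) = 0.9998 for 1 h. Adding first-order absorption lowers the bottom of the range to 0.972.

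**Step 5: is Day 28 late enough?** The fraction of steady state at 28 × 24 = 672 h is 1 − 2^(−672/90) = 0.994 and 1 − 2^(−672/110) = 0.986. On the protocol's half-lives, yes.

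**Step 6: can the pre-dose value replace the missing 24-hour sample?** The linear trapezoidal rule at the planned times, plus a last segment from 12 to 24 h ending at the pre-dose value, gives 0.998 to 1.000 of the model AUC0-24 on Day 28, within about 0.3%. On Day 0, where the pre-dose value is zero, it gives only 0.68 to 0.77. The device works on Day 28 only.

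**Step 7: counting troughs.** Pre-dose samples per subject: Day 0 (no drug yet) and Day 28. On-treatment troughs: one. The Day 28 trough is clearly planned: the flow chart lists ten time points including pre-dose, and Table 2 allots 40 mL in 4 mL tubes, or 10 tubes, to each of D0 and D28. The figure of 10 samples per subject in 5.3.10 and 9.2.1 therefore has to mean per PK day.

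**The case against.** The strongest reply is that nothing is mismeasured. Both sections print 12 h beside the symbol, the window matches the last sample, and AUC0-12 is a legitimate partial area. That stands: the faults are the label and the absence of a 24-hour value.

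Three stronger readings are tempting, and the documents do not support them.

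- A reader might infer that all AUC values come out at about half. The parent is barely touched, and the metabolite fraction on Day 0 differs from that on Day 28.
- A reader might infer that the choice of 50 mg is undermined, because 3.1.1 cites high exposure to the active metabolite. That section also cites earlier safety data, and the choice was made before this trial; this trial's AUC does not feed it.
- A reader might infer that comparison with earlier studies is invalid. The public text of section 1.2.6 shows no content, so the AUC window used there is unknown and the harm is conditional.

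The SAP glossary does define AUCtau over one dosing interval at steady state, but SAP 4.3 excludes PK methods, so that entry governs no planned analysis.

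On steady state, the protocol already gives the half-life argument, and Step 5 supports the Week 4 timing. That also stands. But those half-lives are prior knowledge, and a study looking for PK differences in UC cannot treat them as confirmed by its own data. The same caution applies to the proposed AUC0-24, which must be labelled as resting on assumed steady state.

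**Conclusion.** The point holds as a labelling contradiction plus a check that cannot do its job. Sections 5.3.10 and 9.2.1 must be reconciled with the once-daily regimen. As written, the metabolite value reported as the dosing-interval AUC would be about 50-52% of the 24-hour value at Day 28 (formation from instantaneous to a 4 h half-life, assumed). On Day 0 it would be about 39-52% of AUC0-24 (0.25-4 h, assumed). The parent value would be about 97-100%. All of this relies on the protocol's half-lives holding in UC.

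Day 28 is expected to be at 98.6-99.4% of steady state, so there is no ground for saying that steady state will not have been reached; the planned data simply cannot verify it. The matter is secondary and descriptive, in nine subjects, of whom about six receive ABX464 under 2:1 allocation (9 × 2/3).

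**What to change.** 1. In 5.3.10 and 9.2.1, rename the planned area AUC0-12 on both PK days.
2. For Day 28 only, also report AUC0-24 (τ = 24 h), with the Day 28 pre-dose concentration as the 24-hour value, and state that this assumes steady state.
3. Delete the visual steady-state assessment. State instead that steady state at Day 28 is assumed from the prior half-lives and is not verified in this study.
4. State that the ten PK samples are per PK day.

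The cost is a wording change and one derived parameter, with no new sample.

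Optionally, add a pre-dose PK sample at the already scheduled D56 draw, which would give a second trough after the stated 19 to 22 days. Its price is one extra tube and assay per PK subject, and arranging that the day's capsule is taken after the draw. A D14 trough would not help show a plateau: it precedes those 19 to 22 days, and at 336 h the expected level is 1 − 2^(−336/110) = 88% to 1 − 2^(−336/90) = 92% of steady state.

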5.4. Summary of blood samples

The table 2 below summarizes the volume of blood to be sampled at each study visit.

Table 2: Blood Volume

-	REQUIRED VOLUME	COLLECTION TUBE	SCR D-14	BSL D0	D7	D14	D28	D56	EOS D63	TOTAL
Hematology (Hemoglobin, Hematocrit, Red Cell Count, MCV, MCHC, Platelets, White cell count with diff.)	0.5mL EDTA blood	2mL EDTA tube	2	2	2	2	2	2	2	14
Biochemistry panel incl CRP, GLDG and Serum Pregn.	1.5ml, serum	3.5mL serum gel tube	3,5	3,5	3,5	3,5	3,5	3,5	3,5	24,5
IL22	1mL serum	2.5mL serum gel tube	2,5	2,5	2,5	2,5	2,5	2,5	2,5	17,5
CMV IgG and IgM	0.75mL serum	2.5mL serum gel tube	2,5	Ī						2,5
Quantiferon TB Gold Plus	4mL plasma	4x 1mL tube	4							4
ESR on site	5mL whole blood	SmL ESR tube		5	5	5	5	5	5	30
PK samples	1.0 mL serum	4mL serum tube		40		l	40			80
miRNA-124 samples	2.5mt whole blood	2.5mL PAXgene tube		2,5			2,5	2,5		7,5
		Total per visit	14,5	55,5	13	13	55,5	15,5	13	180

